#### **Baseline value:**

- The parent study baseline is defined as the most recent non-missing measurement (scheduled or unscheduled) collected before the first dose of study drug in the parent study (studies 102 or 103). The parent study baseline will be used to calculate the absolute and relative change from baseline for efficacy analyses unless otherwise specified.
- The TC safety baseline is defined as the most recent non-missing measurement (scheduled or unscheduled) collected before the first dose of study drug in the parent study (if the subject actually received at least one dose of VX-659/TEZ/IVA during the parent study) or the first dose of study drug in the OLS (if the subject did not actually receive at least one dose of VX-659/TEZ/IVA during the parent study). The TC safety baseline will be used in the safety analyses.

**Change (absolute change)** from baseline will be calculated as post-baseline value - baseline value.

**Unscheduled visits:** Unscheduled visit measurements will be included in analysis as follows:

- 1) In scheduled visit windows per specified visit windowing rules
- 2) In the derivation of baseline and last on-treatment measurements
- 3) In the derivation of maximum and minimum values, and maximum and minimum change from baseline values during the analysis period for the safety analyses
- 4) In individual subject data listings as appropriate

**Visit windowing rules:** The analysis visit windows for protocol-defined visits for study 105 are provided in Section 12.1. The visit window for the parent studies are described in the SAP for the individual parent studies.

**Incomplete/missing data** will not be imputed, unless specified otherwise.

**Outliers:** No formal statistical analyses will be performed to detect or remedy the presence of statistical outliers, unless specified otherwise.

**Multiplicity:** There will be no multiplicity adjustment, unless specified otherwise.

### 9.2 Background Characteristics

The analysis described in this section (except for study drug exposure) will be presented separately for subjects from parent studies 102 and 103.

### **9.2.1 Subject Disposition**

A summary table of subject disposition in the OLS will be presented for the OL All Subjects Set by treatment group in the parent studies and overall with the following categories:

- Enrolled (OL All Subjects Set)
- Dosed (OL-SS)
- Enrolled and dosed (OL-FAS)

The number and percentage (based on OL-FAS) of subjects in each of the following disposition categories will be summarized by treatment group in parent studies and overall:

- Completed Treatment
- Prematurely discontinued treatment and the reasons for discontinuation
- Completed study
- Prematurely discontinued the study and the reasons for discontinuation

A listing will be provided for subjects who discontinued treatment during OLS or who discontinued OLS with reasons for discontinuation.

### **9.2.2 Demographics and Baseline Characteristics**

Demographics and parent study baseline characteristics will be summarized based on the OL-FAS and presented by treatment group in parent studies and overall.

Demographic data will include the following:

- Age at parent study baseline (in years)
- Sex (female and male)
- Ethnicity (Hispanic or Latino, not Hispanic or Latino, and not collected per local regulations)
- Race (White, Black or African American, Asian, American Indian or Alaska Native, Native Hawaiian or Other Pacific Islander, Not Collected per Local Regulations and Other)
- Geographic region (North America, Europe [including Israel and Australia])

Parent study baseline characteristics will include the following:

- Weight (kg)
- Height (cm)
- BMI (kg/m^2)
- BMI z-score (for subjects  $\leq 20$  years old at parent study baseline)

Stratification categories (in addition to sex, if applicable) used in the parent study will include the following:

- Age at the Screening Visit of parent study ( $< 18$ , and  $\geq 18$  years)
- ppFEV1 determined during the Screening/Run-in Period of parent study ( $< 70$ , and  $\geq 70$ )

Note that one of the parent studies (study 103) had a 4-week TEZ/IVA run-in period during which the ppFEV1 used in stratification was determined.

Disease characteristics based on parent study baseline will include the following:

- ppFEV1 at parent study baseline (<40, ≥ 40 to <70, ≥70 to ≤90, and >90)
- ppFEV1 at parent study baseline (continuous)
- Sweat chloride at parent study baseline (continuous)
- CFQ-R respiratory symptoms domain score at parent study baseline (continuous)
- Prior use of dornase alfa (Yes, No)
- Prior use of azithromycin (Yes, No)
- Prior use of inhaled antibiotic (Yes, No)
- Prior use of any bronchodilator (Yes, No)
- Prior use of any inhaled bronchodilator (Yes, No)
- Prior use of any inhaled hypertonic saline (Yes, No)
- Prior use of any inhaled corticosteroids (Yes, No)
- Infection with *Pseudomonas aeruginosa* within 2 years prior to screening visit (Positive, Negative) of parent study

Prior medication use definition is same as that for the baseline characteristics summary presented in the parent studies.

No statistical tests will be carried out to evaluate any baseline imbalance between treatment groups.

### 9.2.3 Medical History

Medical history (referenced to the start of parent study) will be coded by using the Medical Dictionary for Regulatory Activities (MedDRA). For the OL-FAS, medical history will be summarized descriptively by treatment group in parent studies and overall and by System Organ Class (SOC) and Preferred Term (PT). The corresponding data listing will also be provided.

### 9.2.4 Prior and Concomitant Medications

Medications will be coded using the World Health Organization-Drug Dictionary and categorized as follows:

- **Prior medication:** any medication that was administered during the 56 days before the first dose date of study drug in the OLS.
- **Concomitant medication:** medication continued or newly received during the OL safety period
- **Post-treatment medication:** medication continued or newly received after the OL safety period.

A given medication may be classified as a prior medication, a concomitant medication, or a post-treatment medication; both prior and concomitant; both concomitant and post-treatment; or prior, concomitant, and post-treatment.

If a medication in the study 105 database has completely missing or partially missing start/stop date and if it cannot be determined whether it was taken before the first dose date of the OLS, concomitantly during the OL safety period, or after the OL safety period, it will be considered in all 3 categories of prior, concomitant, and post-treatment medication. Details for imputing missing or partial start and/or stop dates of medication are described in Section 12.2.

For the OL-FAS, prior medications and concomitant medications will be summarized descriptively by: 1) treatment group in parent studies and overall, preferred name (PN); and 2) treatment group in parent studies and overall, anatomic class (ATC) level 1, ATC level 2, and PN. Post-treatment medications will be listed for each subject.

### **9.2.5 Study Drug Exposure**

Duration of study drug exposure is defined as [last dose date – first dose date + 1 day] within the OL safety period, regardless of any interruption in dosing between the first and the last dose. For the IA, for subjects who are still on study drug at the IA data cutoff date, the IA data cutoff date will be used as the last dose date for the exposure calculation.

Study drug exposure (in weeks) during the OL safety period for the OL-SS will be summarized descriptively by the number of subjects (n), mean, SD, median, min, and max. It will also be summarized into the following categories:  $\leq 24$  weeks,  $>24$  to  $\leq 48$  weeks,  $>48$  to  $\leq 72$  weeks,  $>72$  to  $\leq 96$  weeks,  $>96$  weeks. Additionally, the total study drug exposure, defined as the sum total of the study drug exposure across all subjects (in patient-weeks and patient-years), will be provided. The summary will be by “Any VX-659/TEZ/IVA” group.

### **9.2.6 Study Drug Compliance**

Study drug compliance for the OL efficacy period will be calculated as:  $100 \times [1 - (\text{total number of days of study drug interruption}) / (\text{duration of study drug exposure in days})]$ . A study drug interruption on a given day is defined as an interruption of any study drug on that day.

Percentage of study drug compliance will be summarized based on the OL-FAS and presented by treatment group in parent studies and overall. Percentage of study drug compliance will be summarized descriptively by the number of subjects (n), mean, SD, median, min, and max. It will also be summarized in categories:  $<80\%$  and  $\geq 80\%$  using frequency tables.

In addition, percentage of tablets taken during the OL efficacy period will be calculated using the following formula:  $100 \times [(\text{total number of tablets dispensed}) - (\text{total number of tablets returned})] / (\text{total number of tablets planned to be taken per day} \times \text{duration of study drug exposure in days})$ . Summary similar to those for the study drug compliance will be produced based on the OL-FAS.

### **9.2.7 Important Protocol Deviation**

An important protocol deviation (IPD) is a deviation that may significantly affect the completeness, accuracy, or reliability of the study data or that may significantly affect a subject’s rights, safety, or well-being. IPD rules will be developed and finalized prior to the clinical database lock for study 105.

The protocol deviations that should be considered as potential IPDs include, but are not limited to:

- Subject was enrolled in the study despite the violation of inclusion/exclusion criteria
- Subject was less than 80% compliant with study drug for non-safety reason
- Subject received prohibited concomitant medications
- Subject received the wrong treatment or incorrect doses

Occurrence of any of these events should be considered as potential IPDs, but a team should categorize them as IPDs only if they have the potential to significantly affect the completeness, accuracy, or reliability of the study data or that may significantly affect a subject’s rights, safety, or well-being.

IPDs (from the clinical database or from the site deviation log) during the OL Efficacy period will be summarized descriptively based on the OL-FAS and presented by treatment group in parent studies and overall. Additionally, IPDs during the OL Efficacy period will be provided in an individual subject data listing. IPDs will be analyzed only as part of final analysis.

### 9.2.8 Summary of Analysis of Background Characteristics

Background characteristics that will be analyzed for each analysis set is presented in [Table 9-1](#).

Table 9-1 Analysis of Background Characteristics

Analysis Set	Background characteristics
OL All Subjects Set	Disposition
OL-FAS	Demographics (parent study baseline) Baseline characteristics (parent study baseline) Medical History Prior and Concomitant Medications Study drug compliance Important Protocol Deviation (final analysis only)
OL-SS	Study drug exposure

## 9.3 Efficacy Analysis

The parent study baseline will be used to calculate the change from baseline for continuous efficacy endpoints unless otherwise specified. The efficacy data from subjects with parent study 102 will be presented separately from those with parent study 103. The descriptive summary for continuous endpoints during OL efficacy period will be presented by the treatment groups in the parent study, and restricted to the last visit at which the number of subjects in each treatment group is at least 20.

No model-based analysis (MMRM, Negative Binomial/Poisson, or Time-to-event analysis) will be conducted.

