##### **5.1.2 Secondary Efficacy and Pharmacodynamic Endpoints**

- Absolute change from baseline in percent predicted forced expiratory volume in 1 second (ppFEV1)
- Absolute change in sweat chloride (SwCl)
- Number of pulmonary exacerbations (PEX)
- Time-to-first PEX
- Absolute change in body mass index (BMI)
- Absolute change in BMI z-score
- Absolute change in body weight

- Absolute change from baseline in Cystic Fibrosis Questionnaire-Revised (CFQ-R) respiratory domain score

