### 7.1.3 Cumulative TC Efficacy Set

The Cumulative TC Efficacy Set includes subjects who were randomized to VX-659/TEZ/IVA and received at least one dose of study drug during the parent study and/or received at least one dose of study drug during the OLS. The Cumulative TC Efficacy Set will be used to analyze PEx data on VX-659/TEZ/IVA during the parent study or during study 105. PEx data for subjects from parent study 102 will be presented separately from the PEx data for subjects from parent study 103.

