## 9.3.2 Analysis of Secondary Efficacy and Pharmacodynamic Endpoint

### 9.3.2.1 Definition of Variables

Percent predicted forced expiratory volume in 1 second (ppFEV1): Percent predicted FEV1 is the ratio of FEV1 (L) and predicted FEV1 (L), expressed as a percentage. See Section 12.6 for more details.

Sweat chloride (SwCl): the SwCl value for a given visit will be calculated as the mean of the non-missing sweat chloride measurements obtained on the left and right arms at that visit. If one of the two arm measurements at a time point is missing, the other will be used as the mean. A volume  $\geq 15$   $\mu\text{L}$  is required for an accurate determination of sweat chloride. Any results reported as having volume  $< 15$   $\mu\text{L}$  will be considered missing. Any sweat chloride values reported as  $< 10$  mmol/L or  $> 160$  mmol/L will be considered missing.

Pulmonary exacerbation (PEX): A PEX is defined as a new event or change in antibiotic therapy (IV, inhaled, or oral) for any 4 or more of the following signs/symptoms:

- Change in sputum
- New or increased hemoptysis
- Increased cough
- Increased dyspnea
- Malaise, fatigue, or lethargy
- Temperature above 38°C (equivalent to approximately 100.4°F)
- Anorexia or weight loss
- Sinus pain or tenderness
- Change in sinus discharge
- Change in physical examination (PE) of the chest
- Decrease in pulmonary function by 10%
- Radiographic changes indicative of pulmonary infection

The number of PEX is then defined as the total number of PEX for each treatment group during the cumulative TC Efficacy period.

The time to first PEX is the number of days from the start of the cumulative TC Efficacy period to the date of the first pulmonary exacerbation during the cumulative TC Efficacy period. A subject who does not experience a PEX during the cumulative TC Efficacy period will be censored at the cumulative TC Efficacy period end date.

Body mass index (BMI): the BMI at each visit is calculated using the weight and height at each visit as follows:

$$\text{BMI} = \frac{\text{Weight (kg)}}{\text{Height}^2 (\text{m}^2)}$$

BMI z-score: the BMI score, adjusted for age and sex, will be referred to as BMI-for-age z-score (BMI z-score). The BMI z-score will be calculated by using Centers for Disease Control and Prevention (CDC) growth charts, with the age (in months) used for the calculation defined in Section 12.1.

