### **9.3.2.2 Analysis Method**

For ppFEV1, sweat chloride, BMI, BMI z-score, body weight, and CFQ-R respiratory domain score, the raw value and change from parent study baseline will be summarized for each visit during the OL efficacy period for the OL-FAS.

The number of PEx during the cumulative TC Efficacy Period will be summarized for the cumulative TC Efficacy Set, by treatment group and overall for subjects from Study 102 and by overall for subjects in Study 103. In addition, the total number of PEx, PEx requiring hospitalization, PEx requiring IV antibiotic therapy, and PEx requiring hospitalization or IV antibiotic therapy will be summarized similarly.

[figure not shown]

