### **9.3.2.3 Sensitivity and Supportive Analysis of Secondary Endpoints**

No sensitivity or supportive analysis is planned for the secondary endpoints.

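### PEx totals by Study 102 treatment group are planned without person-time, although the SAP gives the two groups different follow-up by design

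*SAP*

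**What the plan says.** **Statistic.** SAP 9.3.2.1: "The number of PEX is then defined as the total number of PEX for each treatment group during the cumulative TC Efficacy period". SAP 9.3.2.2: "The number of PEx during the cumulative TC Efficacy Period will be summarized for the cumulative TC Efficacy Set, by treatment group and overall" for Study 102, and overall only for Study 103. PEx involving hospitalisation or IV antibiotics are handled in the same way.

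**Who is in the set.** Under SAP 7.1.3, a subject enters by having been "randomized to VX-659/TEZ/IVA and received at least one dose of study drug during the parent study", or by receiving at least one dose in Study 105. Placebo subjects can enter only by the second route.

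**Observation time.** Under SAP 8.2, TC-randomised subjects are counted from their first parent-study dose through Study 105, or over the parent study's efficacy period alone if they did not enrol. Subjects not randomised to TC are counted from their first Study 105 dose. Any uncollected gap between the parent follow-up visit and Study 105 consent is left out of the period.

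**Person-time elsewhere.** SAP 9.2.5 gives patient-weeks and patient-years, but for the pooled open-label safety set over the OL safety period. SAP 9.4.1 specifies exposure-adjusted rates for adverse events only.

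**Models and supportive work.** SAP 9.3: "No model-based analysis (MMRM, Negative Binomial/Poisson, or Time-to-event analysis) will be conducted". SAP 9.3.2.3: "No sensitivity or supportive analysis is planned for the secondary endpoints". Protocol 12.3.3.2 had planned negative binomial regression for the number of PEx and a Kaplan-Meier display for time to first PEx. SAP section 3 attributes the removal of analyses to the early end of the study.

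**Time to first PEx.** It remains in the SAP 5.1.2 list ("Time-to-first PEX"). SAP 9.3.2.1 still defines it: "The time to first PEX is the number of days from the start of the cumulative TC Efficacy period", and subjects without an event "will be censored at the cumulative TC Efficacy period end date". SAP 9.3.2.2 plans no output for it.

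**The concern.** A total count can be read only against the time over which it was collected. Here the two Study 102 columns cover different spans by construction. The TC column includes parent-study time, and it includes subjects who never entered Study 105. The placebo column includes neither. A reader who sees the two totals next to each other cannot tell how much of any difference is PEx frequency and how much is follow-up. Nothing else in the visible plan supplies the missing denominator: the planned patient-years belong to another set and another period and are not split by parent-study group.

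At stake is the interpretability of one secondary, descriptive efficacy table.

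**Working it through.** **The plan's own PEx figure.** SAP 6.2 states a 95% CI half-width below 6% for cumulative PEx incidence of 30% with over 400 subjects. With n = 400: 1.96 × √(0.30 × 0.70 / 400) = 0.0449, or 4.5%. The statement reproduces and is not in dispute. It concerns an incidence proportion, so it gives no denominator for the group totals.

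**Inputs for the illustration.** None of these is in the documents; all are assumptions.
- P, time in Study 102 counted for TC subjects: 4, 12 or 24 weeks.
- T, time in Study 105 at termination: 24, 48 or 96 weeks.
- f, share of dosed subjects who roll over, the same in both arms: 1.00 or 0.90.
- N, subjects dosed per arm, equal in both arms; r, PEx rate, equal and constant.
- TC subjects who do not roll over contribute the full P.

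**Formula.** Expected totals under SAP 7.1.3 and 8.2:
- TC: rN[f(P + T) + (1 − f)P] = rN(P + fT)
- Placebo: rN·fT
- Ratio of totals, TC : placebo = 1 + P/(fT)

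| P (weeks) | f | T = 24 | T = 48 | T = 96 |
|---|---|---|---|---|
| 4 | 1.00 | 1.17 | 1.08 | 1.04 |
| 12 | 1.00 | 1.50 | 1.25 | 1.13 |
| 24 | 1.00 | 2.00 | 1.50 | 1.25 |
| 4 | 0.90 | 1.19 | 1.09 | 1.05 |
| 12 | 0.90 | 1.56 | 1.28 | 1.14 |
| 24 | 0.90 | 2.11 | 1.56 | 1.28 |

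**Worked cases** (assumed N = 100 per arm, r = 0.5 PEx per patient-year, f = 0.90, 52 weeks per year):
- P = 24, T = 24. TC: (100 × 24 + 90 × 24)/52 = 87.7 patient-years, 43.8 PEx. Placebo: (90 × 24)/52 = 41.5 patient-years, 20.8 PEx. Ratio 2.11.
- P = 4, T = 96. TC: (100 × 4 + 90 × 96)/52 = 173.8 patient-years, 86.9 PEx. Placebo: (90 × 96)/52 = 166.2 patient-years, 83.1 PEx. Ratio 1.05.

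PEx per patient-year is 0.5 in both groups in both cases. That follows from assuming an equal constant rate. It shows what the denominator removes and says nothing about the actual rates.

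**When the ratio could fall below 1.** With different rollover shares the ratio is (P + f_TC·T)/(f_PBO·T). It is below 1 only if f_PBO exceeds f_TC + P/T. At P = 4 and T = 96, P/T = 0.042, so with f_TC = 0.90 placebo rollover would have to exceed 0.942. At P = T it cannot happen. Unequal arm sizes would also shift the ratio.

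**The case against.** The strongest reply is that nothing in the plan compares the groups. Study 105 is a single open-label cohort, efficacy has been cut to descriptive summaries, and Table 7-1 says the labels only record parent-study assignment. That is correct and it limits the severity. It does not answer the point, because the SAP itself chooses to split the totals by Study 102 group, and a descriptive total over unequal time is still hard to read.

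It can also be said that P, T and f are all assumed. They are, so the ratios show only what could happen. That observation time differs follows from SAP 8.2 without any of them.

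Three stronger readings are tempting, and the documents do not support them:

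- *The direction of the distortion is unknown.* Values below 1 arise if one works with PEx per subject in the set: that ratio is P/T + f, which reaches 0.94 at P = 4, T = 96, f = 0.90. The SAP, however, defines the endpoint as a group total. For totals with equal numbers dosed and equal rollover, the ratio is always above 1; a reversal needs unequal rollover or arm sizes.
- *Time to first PEx was dropped without a decision.* SAP 9.3 bars time-to-event analysis, this is the only such endpoint in the SAP 5.1.2 list, and section 3 gives early termination as the general reason. What remains is a listing and a definition that were not reconciled with that sentence.
- *The Kaplan-Meier display must be restored.* It is not model-based, and early termination does not by itself prevent it. But how informative it would be cannot be judged from the documents, and omitting it is a sponsor trade-off. Nor does it matter at present that SAP 9.3.2.1 is silent on subtracting gap days from time to first PEx, since no planned output uses that variable.

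**Conclusion.** The person-time point stands. Group totals of PEx are planned over a period whose length differs between the two Study 102 groups by definition, and no denominator is planned for that set and period. On the assumed grid, equal PEx rates would give a TC total 1.04 to 2.00 times the placebo total at full rollover, and 1.05 to 2.11 times at 90% rollover, given equal numbers dosed and equal rollover in both arms. The true size depends on follow-up, arm sizes and rollover, which the documents do not report.

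This is worth correcting because it is cheap and improves the table, but it is a secondary, descriptive matter. The retained listing and definition of time to first PEx is an editorial inconsistency only.

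**What to change.** **SAP 9.3.2.2.** Beside each PEx count, report total person-time in the Cumulative TC Efficacy Period, with the gap excluded as SAP 8.2 already requires, and PEx per patient-year. Do this by Study 102 treatment group and overall, and overall for Study 103.

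Add one sentence: the Study 102 groups are not a randomised comparison in this table, because TC subjects enter the set after a single parent-study dose, while placebo subjects enter only if dosed in Study 105. The rate corrects for length of observation, not for this selection.

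**Editorial, SAP 5.1.2 and 9.3.2.1.** State that time to first PEx will not be analysed because of early termination. A descriptive Kaplan-Meier display with numbers at risk is optional. If it is added, 9.3.2.1 should say that gap days are subtracted.

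**Cost.** Two table rows and one sentence, plus a short statement for the editorial point. No new data are needed, since SAP 8.2 already defines the start, end and gap of the period.
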